8.3. Sample size

This pilot study will enroll 40 participants into treatment. This sample size is considered to be achievable. We have calculated precision estimates based on various rates of primary endpoint of efficacy [loss of HBeAg and HBV DNA $\leq 1,000$ IU/mL at the end of follow-up (week 96)]. For example, if the expected proportion achieving primary efficacy endpoint is 25%, then we would be able to estimate it with 95% Clopper-Pearson confidence to ensure that the expected width of the interval does not exceed 29% (or equivalently, the estimated 95% confidence limits will be within $\pm 15\%$ of the estimate). Below are some further precision estimates:

Table: Precision (Width) Estimates for 95% Confidence Intervals under Different Primary Endpoint Proportions

Expected proportion with primary efficacy endpoint	95% lower	95% upper	Width
0.15	0.057	0.298	0.24
0.20	0.091	0.356	0.27
0.25	0.127	0.412	0.29

0.30	0.166	0.465	0.30
------	-------	-------	------

9. Data and safety monitoring board

Data and safety will be monitored by the National Institute of Diabetes and Digestive and Kidney Diseases (NIDDK) in conjunction with an NIDDK-appointed Data and Safety Monitoring Board (DSMB). This board serves in a consultative capacity to inform the NIDDK decisions regarding conduct of the study. The description of DSMB activities is included in the DSMB Charter.

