8.1.1. Analysis of primary endpoints

The primary endpoints include safety, measured by the rate of adverse and Serious Adverse Events, and efficacy, defined as loss of HBeAg and HBV DNA $\leq 1,000$ IU/mL at the end of follow-up (week 96). That is, only participants achieving HBeAg loss and having HBV DNA ≤ 1000 IU/mL at the end of follow-up will be considered as achieving the primary efficacy endpoint.

Safety

Summaries of adverse events (number of adverse events, number and percentage of participants with at least one adverse event, and for each adverse event, rate per person-years) will be provided. Events will be summarized based on the date of onset for the event. A treatment emergent adverse event will be defined as an adverse event that begins on or after the date of first dose of study drug.

Summaries of the following are planned:

- all adverse events recorded between screening and first dose of study medication,
- all treatment emergent adverse events,
- all emergent and related adverse events,
- all treatment emergent renal adverse events,
- all treatment emergent and related renal adverse events
- combined Grade 2, 3 and 4 treatment emergent adverse events,
- combined Grade 2, 3 and 4 related treatment and emergent adverse events,
- combined Grade 3 and 4 treatment emergent adverse events,
- combined Grade 3 and 4 related treatment and emergent adverse events,
- all adverse events that caused permanent discontinuation of study drug,
- all adverse events that caused temporary interruption of study drug,
- all serious adverse events, and
- all serious and related adverse events.

We will provide 95% confidence intervals for the rate of adverse and serious adverse events.

Efficacy

The percentage of participants achieving the primary efficacy endpoint will be summarized with the point estimate and 95% confidence interval.

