Adverse events and Serious Adverse Events (SAE) that do not meet expedited reporting	Quarterly reports for NIDDK and the appropriate oversight committees

criteria

Serious Adverse Events that meet expedited reporting criteria

As they occur for NIDDK, DSMB, appropriate industry partner(s), and cumulative reports quarterly

Yearly for DSMB

Laboratory data

Definitions of adverse and serious adverse events and their management guidelines are provided in section 7.5 of this protocol along with the reporting procedures and in the MOP. No interim analysis for efficacy is planned.

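### Section 8.3 states that the exact 95% limits at a 25% response lie within ±15 points of the estimate, but the plan's own table puts the upper limit 16.2 points above it

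*Combined protocol and SAP*

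**What the plan says.** The sample-size section (8.3) fixes the size of the single arm: "This pilot study will enroll 40 participants into treatment". The first reason given is feasibility: "This sample size is considered to be achievable". Precision follows, with a worked case: "For example, if the expected proportion achieving primary efficacy endpoint is 25"%. For that case the plan names the 95% Clopper-Pearson interval and says the sample size serves "to ensure that the expected width of the interval does not exceed 29"%. A parenthesis then restates this: "or equivalently, the estimated 95% confidence limits will be within" ±15% of the estimate.

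Below the sentence stands a table headed "Table: Precision (Width) Estimates for 95% Confidence Intervals under Different Primary Endpoint Proportions". Its row for 0.25 gives a lower limit of 0.127, an upper limit of 0.412 and a width of 0.29.

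Section 8.1.1 describes the primary efficacy analysis: "The percentage of participants achieving the primary efficacy endpoint will be summarized with the point estimate and 95% confidence interval".

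**The concern.** The parenthesis presents a total width of 29 points and a distance of at most 15 points to each limit as the same statement. That would be true of an interval centred on the estimate, where half of 29 is 14.5, or about 15. The Clopper-Pearson interval is not centred on the estimate when the proportion is well below one half: the upper limit lies farther away than the lower one. A correct width can therefore go with an upper limit outside ±15 points, and the table row for the same example shows this.

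What is at stake is limited. The plan specifies no hypothesis test for efficacy, so precision is the only statistical support offered for 40 participants, alongside feasibility. The ±15% clause is the short form of that precision and it errs on the optimistic side. It implies an upper limit of at most 40%, whereas the table shows 41.2%.

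**Working it through.** **Inputs**

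- n = 40, expected proportion 25% (x = 10 responders), two-sided 95% Clopper-Pearson interval: section 8.3.
- Stated bounds: width at most 29 points, each limit within ±15 points: section 8.3.
- Missing week-96 outcomes count as failures (section 8.2), so the denominator stays at 40.

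**Formula**

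Lower limit = 0.025 quantile of Beta(x, n − x + 1). Upper limit = 0.975 quantile of Beta(x + 1, n − x).

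**Step 1: reproduce the plan's table (n = 40)**

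| Proportion | x | Lower | Upper | Width | Distance below | Distance above |
|---|---|---|---|---|---|---|
| 0.15 | 6 | 0.0571 | 0.2984 | 0.2413 | 0.0929 | 0.1484 |
| 0.20 | 8 | 0.0905 | 0.3565 | 0.2660 | 0.1095 | 0.1565 |
| 0.25 | 10 | 0.1269 | 0.4120 | 0.2850 | 0.1231 | 0.1620 |
| 0.30 | 12 | 0.1656 | 0.4653 | 0.2997 | 0.1344 | 0.1653 |

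All four rows agree with the printed limits and widths to rounding.

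**Step 2: test the ±15 clause at 25%, from the printed row alone**

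- Above: 0.412 − 0.25 = 0.162, which exceeds 0.15 by 0.012.
- Below: 0.25 − 0.127 = 0.123, which is inside 0.15.
- Half-width: 0.2850 / 2 = 0.1425. This is inside 0.15, but it is the distance to neither limit.

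**Step 3: read the clause as an expectation**

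The preceding words refer to an expected width, so each quantity was also averaged over X ~ Binomial(40, 0.25), with distances measured from the observed X/40:

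- mean width 0.2808 (the claim of at most 29% holds);
- mean distance below 0.1208;
- mean distance above 0.1599, about 1.0 point over the bound.

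**Step 4: how often the bound fails on the upper side**

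The distance above is 0.1484 at 6/40 and 0.1528 at 7/40. It is 0.1514 at 24/40 and 0.1477 at 25/40. It exceeds 0.15 at every count from 7 to 24. With a true rate of 25%, P(7 ≤ X ≤ 24) = 0.904.

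**Step 5: other readings**

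- *±15% relative to the estimate:* 0.15 × 25 = 3.75 points, so the mismatch would be far larger.
- *Another interval method at 10/40:* the distance above is 13.4 points for Wald, 14.8 for Jeffreys, 15.2 for Wilson and 15.4 for Agresti-Coull. Wald and Jeffreys would satisfy the clause, but the sentence names Clopper-Pearson and the table matches that method.

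**The case against.** The strongest defence is that the clause is only a rounded half-width. It follows a total width of 29% and the word equivalently; half of 29% is 14.5%, and the true half-width is 14.25 points, so ±15 would even be slightly conservative. This probably explains where the figure came from. It does not make the sentence true, because the sentence speaks of where the confidence limits will lie, and one of them lies outside.

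The second defence is that nothing follows from the error. The correct limits stand in the table just below, the final interval will be computed from the data, no success threshold is set, and section 9.1 states "No interim analysis for efficacy is planned". All of this stands, and it is why the point is minor.

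The third is that a 90.4% failure probability sounds worse than the miss it counts. That is fair: at 7/40 the upper distance is 15.28 points, which rounds to 15. If only distances above 15.5 points are counted, the probability is 81.8%, and the largest upper distance at any count is about 16.7 points. The probability shows that the failure is the usual outcome at a 25% true rate, but the excess is at most 1.7 points.

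**Conclusion.** The concern holds. At 25% with 40 participants the exact upper limit is 16.2 points above the estimate against a stated bound of 15, an excess of 1.2 points (1.0 on average over the binomial distribution). The lower limit, 12.3 points below, meets the bound.

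The plan makes the ±15 statement for the 25% example only. For context, the printed upper limits lie 14.8, 15.6 and 16.5 points above 0.15, 0.20 and 0.30.

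The conclusion rests on the plan's own choices (Clopper-Pearson, 95%, n = 40) and on reading ±15% as percentage points, the reading most favourable to the plan. The 29% width and the table are correct. This is a minor correction to a planning figure, with no effect on the sample size or the analysis.

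**What to change.** In section 8.3, delete the parenthesis that begins with *or equivalently*, including the ±15% figure. Put in its place: *the exact 95% limits will lie about 12 points below and 16 points above an estimate of 25%*. Both figures come from the plan's own table row. If a single number is preferred, a half-width of about 14 points is accurate, provided it is called a half-width and not a bound on each limit. Keep the 29% expected width, the table and the 40 participants. The cost is one clause in one sentence.

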9.1. Data and Safety Monitoring

This trial aims to examine the safety and efficacy of treatment with 8 weeks of entecavir followed by 40 weeks of both entecavir and peginterferon alfa-2a in the treatment of chronic hepatitis B in HBeAg positive adults who are in the immune tolerant phase. The individual drugs (peginterferon alfa-2a and entecavir) are FDA-approved and have been well-studied except in the immune tolerant participants. The risks to participants are outlined in sections 5.2.3 and 5.3.3 of this protocol. Section 7 of the protocol defines the toxicities associated with these drugs and outlines dose adjustment and discontinuation guidelines due to toxicity. The data and safety monitoring plan (DSMP) for this study focuses on close monitoring by the principal investigators (PI) and prompt reporting of excessive adverse events and all serious adverse events to the DCC and the appropriate oversight committees or entities such as the NIDDK, the Data and Safety Monitoring Board and to the participating centers' IRBs.

The Data Coordinating Center (DCC) will monitor clinical center performance (e.g., recruitment, retention, data completeness, timeliness of data collection and submission) and protocol compliance. These reports, with summaries of adverse event data, will be provided to the DSMB for their quarterly reports and biannual calls or meetings, and to the Steering Committee at its annual meeting.

The DCC will work with the HBRN Safety Officer and the Steering Committee to maintain a cumulative summary of adverse events (overall and stratified by serious/non-serious status) that will be forwarded to the DSMB every three months. Safety reports will also be sent to the Principal Investigators and the NIDDK Project Officers. The Project Coordinator will be responsible for distributing these reports and assuring that all parties obtain copies of these reports.

The frequency of data review for this study differs according to the type of data and can be summarized in the following table:

Data type	Frequency of review
Recruitment	Quarterly reports for NIDDK and the appropriate oversight committees
Retention	Quarterly reports for NIDDK and the appropriate oversight committees
Protocol adherence(e.g., meeting inclusion/exclusion criteria, treatment compliance)	Quarterly reports for NIDDK and the appropriate oversight committees
Pregnancy in female subjects receiving treatment	Quarterly reports for NIDDK and the appropriate oversight committees
Adverse events and Serious Adverse Events (SAE) that do not meet expedited reporting	Quarterly reports for NIDDK and the appropriate oversight committees

criteria

Serious Adverse Events that meet expedited reporting criteria

As they occur for NIDDK, DSMB, appropriate industry partner(s), and cumulative reports quarterly

Yearly for DSMB

Laboratory data

Definitions of adverse and serious adverse events and their management guidelines are provided in section 7.5 of this protocol along with the reporting procedures and in the MOP. No interim analysis for efficacy is planned.

9.2 Participant confidentiality

The central database of the study is on a server at the Epidemiology Data Center (EDC) in the Graduate School of Public Health at the University of Pittsburgh secured behind locked doors and an alarm with password access provided only to authorized personnel. Backups are performed daily to guard against data loss due to an equipment or power failure. Scheduled backups and archives at the EDC protect central and local information from hard disk failures. Tape backup volumes and CD-ROM copies of critical project files are located in a secured off-site storage area to prevent data loss due to catastrophic events. Routine virus detection is also enforced for all EDC computers involved in the study. All critical information regarding database transactions is logged and stored in journal files. In the event of accidental corruption of the project database, a previous database state may be restored from backup volumes or journal files. All servers used for this project are connected to uninterrupted power supplies to protect equipment against electrical surges and outages. A secured, computer room in an area with a burglar alarm houses all project server equipment.

Participant confidentiality is preserved by encoding subject names into alphanumeric IDs at the clinical centers. Data sent to the DCC are identified by alphanumeric ID only. No reports of this study will use names or other identifying information such as social security numbers or addresses. Data, with alphanumeric ID only, will be stored at the DCC indefinitely. In addition, following the completion of the study data and information, with alphanumeric ID only, will be submitted in the NIDDK repository by a suitable date agreed upon by NIDDK and the steering committee.

References

Appendix I: Schedule of events for treated participants

Phase of Study	Screening				Treatment										Follow-up			
	-28 to -52	-6 to -28	up to -6	0 ¹	8	1 ²	1 ²	6	2 ⁰	2 ⁴	3 ⁰	3 ⁶	4 ²	4 ⁸	5 ²	6 ⁰	7 ²	9 ⁶
Weeks of Study	-28 to -52	-6 to -28	up to -6	0 ¹	8	1 ²	1 ²	6	2 ⁰	2 ⁴	3 ⁰	3 ⁶	4 ²	4 ⁸	5 ²	6 ⁰	7 ²	9 ⁶
Informed consent			X															
Medical history			X															
Physical exam			X	X	X	X	X	X	X	X	X	X	X	X				X
Drug dispensing				X	X	X	X	X	X	X	X	X	X					
Adherence assessment/ Clinical evaluation including AEs, concomitant meds				X	X	X	X	X	X	X	X	X	X	X	X	X	X	X
Anthropometric measures					X										X			X
Questionnaires (QOL)					X	X									X			X
Health behaviors					X										X			X
Depression assessment			X		X	X				X		X		X		X		X
Symptom questionnaire					X	X	X	X	X	X	X	X	X	X	X	X	X	X
Fatigue questionnaire					X													X
CBC, including platelets and differential ²			X	X	X	X	X	X	X	X	X	X	X	X	X	X	X	X
Hepatic tests (AST, ALT, and bilirubin; albumin and ALKP day 0 and weeks 48 and 96 only) ³	X ⁴	X ⁴	X	X	X	X	X	X	X	X	X	X	X	X	X	X	X	X
Other chemistries (glucose, total protein)			X												X			X
TSH			X			X				X		X		X		X		X
Renal tests (Creatinine and CrCl calculated MDRD)			X	X	X	X	X	X	X	X	X	X	X	X	X	X	X	X
Urinalysis			X	X	X										X			X
PT/INR			X	X											X			X
AFP			X															
Pregnancy test (urine or blood) ⁵			X	X	X	X	X	X	X	X	X	X	X	X				

Phase of Study	Screening				Treatment												Follow-up			
	-24 to -52	-6 to -24	up to -6	0 ¹	8	1	1	2	2	3	3	4	4	5	6	7	9			
Weeks of Study				0 ¹	8	1	1	2	0	0	6	2	8	2	0	2	6			
HBsAg				X										X			X	X		
HBsAg quant					X	X	X	X	X	X	X	X	X	X	X	X	X	X		
HBeAg				X	X	X	X			X		X		X		X	X	X		
HBeAg quant					X	X	X	X	X	X	X	X	X	X	X	X	X	X		
Anti-HBe ⁶					X									X				X		
Quant HBV DNA	X ⁴			X	X	X	X	X	X	X	X	X	X	X	X	X	X	X		
Anti-HBs ⁶					X									X				X		
HBV genotype and subtype ⁷					X															
HBV precore/BCP					X													X		
Antiviral drug resistance mutation testing ⁹⁸					X										X					
Anti-HCV ⁹					X															
Anti-HDV ⁹					X															
Anti-HIV					X										X					
Abdominal imaging ¹⁰					X						X				X			X	X	
Plasma/serum banking ¹¹					X	X	X	X	X	X	X	X	X	X	X	X	X	X		
DNA Banking ¹²					X															

¹. Day 0 is the Baseline visit, and start of study drug.

². CBC to include differential count up to week 48.

³. If total bilirubin elevated, obtain direct bilirubin at next blood draw.

⁴. Historical data acceptable—ALT (2 values, one 28-52 weeks before screening, one 6-28 weeks before screening) and HBV DNA (1 value, within 12-52 weeks before screening).

⁵.

All women with reproductive potential prior to baseline visit; women on treatment with reproductive potential after start of treatment .

⁶. Anti-HBe/Anti-HBs to be done at next visit if HBeAg/HBsAg becomes negative.

⁷. For those who did not have genotype performed for the cohort study

⁸. Also if meets criteria for virologic breakthrough (results not available in real-time).

⁹. Anti-HCV and anti-HDV, if results within 144 weeks of baseline visit are available, tests do not need to be repeated.

¹⁰. Patients with AFP >20 should be further evaluated by imaging (US/CT/MRI) as clinically needed to rule out HCC before entry into the study. Patients meeting AASLD criteria for HCC surveillance should have follow-up imaging per standard of care.

¹¹. 24mL of whole blood (for serum) and 8mL of whole blood (for plasma) at screening visit, day 0, 8, 48 and 96, and 8mL of whole blood (for serum) and 8mL of whole blood (for plasma) at other time points. These volumes include blood that will be collected for central testing. Patients who will be enrolled in HBRN Cohort Study concurrent with screening visit for this trial will have an additional 8 mL serum and 8 mL plasma at the baseline visit for future research.

¹². 5 mL of whole blood if DNA sample (with consent) not previously collected. May be collected at any study visit if not at baseline.

Appendix II: Dosing of peginterferon if missed doses

Dose delayed 1 or 2 days: administer on usual dosing day of the week (e.g., if Monday is the usual dosing day and the dose is delayed until Wednesday, the next dose may be administered as usual on Monday).

Dose delayed 3-5 days: administer subsequent doses every 5th or 6th day until the participant is back to his or her original schedule (e.g., if Monday is the usual dosing day and the dose is delayed until Saturday, the next dose should be administered on Thursday, the following dose on Tuesday, then the dose after that as usual on Monday).

Dose delayed 6 days: hold the dose for that week then continue on the usual schedule the following week (e.g., if Monday is the usual dosing day but the participant is not ready to be dosed until the following Sunday, the dose is considered to have been held and the next injection should be for the following weeks; dose on Monday).

Dose delayed 7 or more days: the investigator may reintroduce study drug at any time and, if necessary, dose the participant every 5th or 6th day until the participant resumes weekly dosing on their usual scheduled day.

Appendix III: Peg-Interferon Dose Reduction

Peginterferon alfa-2a dose adjustment guidelines

Specific dose adjustment guidelines for peginterferon alfa-2a are provided in the tables below for neutropenia, and thrombocytopenia. For other adverse effects considered to be possibly related to peginterferon, including laboratory abnormalities, adverse events, and vital signs changes, investigators should utilize the table below labeled "General Dose Reduction Guidelines." When practicable, abnormal laboratory results should be confirmed as soon as possible following notification of the investigator. If appropriate, downward adjustments in one level reductions should be considered. The lowest dose of peginterferon alfa 2a that should be administered is 45 µg weekly. It should be kept in mind that whereas these guidelines should be generally followed to promote consistency across centers, other responses by an investigator may be more appropriate in some circumstances.

a. General dose reduction guidelines

For Peginterferon alfa-2a, 1 dose reduction = 135 µg; 2 dose = 90 µg; 3 dose = 45 µg

Number of Dose Reduction Levels					
Mild	Moderate Limited	Moderate Persistent	Severe Limited	Severe Persistent	Life-Threatening
0	0	0-1	0-1	1-3	Stop drug

b. Dose adjustments for low absolute neutrophil and platelet counts

Parameter	Downward Dose Adjustment or Delay in Dosing
ANC (cells/mm³)	
≥500	No change
250-499	1 step initially; potentially up to 3 steps
<250	Stop drug
Platelet Count (cells/mm³)	
>50,000	No change
25,000-50,000	1 step initially; potentially up to 3 steps
<25,000	Stop drug

